10. BENEFITS

The study will help determine the best surgical field for endoscopic sinus surgery which will lead to optimal sinus surgery with the best result for the patient in the future.

11. PRIVACY AND CONFIDENTIALITY

All participant information and specimens are handled in compliance with the Health Insurance Portability and Accountability Act (HIPAA) and privacy policies of Stanford University, Stanford Health Care, and Stanford Children's Health.

## 1. STATISTICAL METHODS

A prestudy power analysis was completed with Monte Carlo simulations to estimate the necessary sample size. A sample size of 38 patients in total would give the power of 82% with type I error of 0.05 to detect the difference in Wormald scale between the 2 groups. Patient-level demographics and baseline clinical factors were summarized with mean (standard deviation) for continuous variables and with n (%) for categorical variables. The comparisons of clinical variables (all continuous) between both sides of the nose were performed using paired t test. To estimate the effect of 1% lidocaine with 1:100,000 epinephrine, we constructed a mixed effect models with random slope by accounting for within-subject correlation. All the models were adjusted for age, gender, preoperative Lund-Mackay score, preoperative Lund-Kennedy score, and medication use. Surgery time was found to be right-skewed; therefore, it was log-transformed in the model, and the regression coefficient was exponentiated to represent the percentage difference. We performed reliability testing for the Wormald scale graded by 2 graders, by calculating the intraclass correlation coefficient (ICC) as well as its 95% confidence interval (CI).

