2. STUDY PROCEDURES

a. Procedures

We will first perform chart review to screen for patients who were scheduled for endoscopic sinus surgery for rhinosinusitis that meet both our inclusion and exclusion criteria. We will check the date of the patient's next visit to meet them and explain the study protocol and ask for their consent. If they consent to the study, on the day which they have the surgery we will follow the protocol, giving topical adrenaline on both side and infiltrating lateral nasal wall with the medication according to the study (patient will receive 1% xylocaine with adrenaline (1:100,000) on one side and saline on the contralateral side, they will be randomized to which side receive which solution for infiltration). The Estimated blood loss on each side and the duration of the surgery on each side will also be recorded. The Video of the surgery will be evaluated by 2 different otolaryngologists to give grading score for surgical field of view using Wormald Surgical

Field Grading Scale. Patients will have regular post operative follow up as for endoscopic sinus surgery. At the patient's first follow up at 1 week after the surgery, the patient will be asked to fill out a questionnaire about the postoperative bloody discharge they experienced.

b. Procedure Risks

Any medications may lead to inadvertent effects, however the use of infiltration of xylocaine with adrenaline is widely accepted and has originally been used in preparation for endoscopic sinus surgery and also for variety of surgical procedures both under general and local anesthetic. With correct route and dosage given, infiltration performed by specialist under a well-controlled circumstance as under general anesthesia where patient's vital signs are closely monitored we believe that it is safe to perform the procedure. Topical adrenaline has recently gained popularity among a number of surgeons world wide in the use for endoscopic sinus surgery and has known to be safe and potent with great result in bleeding control.

c. Use of Deception in the Study

Deception will not be used to enroll the patient. We will not perform the procedure without the patient's consent.

d. Use of Audio and Video Recordings

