8. PARTICIPANT POPULATION

a. Planned Enrollment

- (i) 40 participants to be enrolled at Stanford
- (ii) total of 40 participants overall (the study will only be performed at Stanford)
- (iii) the participants will be the patients from the rhinology clinics who have sinusitis that have failed medical treatment and were scheduled for endoscopic sinus surgery

b. Age, Gender, and Ethnic Background

Age range 18-75 years old Both males and females All ethnic backgrounds

c. Vulnerable Populations

Potentially vulnerable subjects (including children, pregnant women, economically and educationally disadvantaged, decisionally impaired, homeless people, employees and students) will not be enrolled in the study.

d. Rationale for Exclusion of Certain Populations

Women and minorities are included, however children are not included since endoscopic sinus surgery is not widely perform in children.

e. Stanford Populations

The study will not involve participants who are laboratory personnel, employees and students.

f. Healthy Volunteers

We do not take healthy volunteers for the study since they would have no indications for the surgery.

g. Recruitment Details

We will identify the participants for recruitment by chart review prior to their preoperative visit. No flyers or other advertisement will be used in the study.

h. Eligibility Criteria

i. Inclusion Criteria

1. Patients between the age of 18-75 years old who were diagnosed with recurrent acute or chronic rhinosinusitis that are recalcitrant to medical treatment and were scheduled for endoscopic sinus surgery

ii. Exclusion Criteria

- 1. Patients who have asymmetrical disease on the two sides (Lund Mackay score difference of 2 or more)
- 2. Patients who have endoscopic sinus surgery for treatment of tumor or disease other than sinusitis
- 3. Patients with nasal polyps
- 4. Patients with underlying uncontrolled hypertension
- 5. Patients with bleeding disorder or are unable to discontinue antiplatelet or anticoagulant before the surgery
- 6. Patients who are allergic to adrenaline or to xylocaine
- 7. Patients who are not consent to the procedure

i. Screening Procedures

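### Does the random slope named in the SAP's mixed model misfit outcomes with one value per side, such as surgery time?

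*SAP*

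**What the plan says.** SAP section 1 gives unadjusted comparisons first: "The comparisons of clinical variables (all continuous) between both sides of the nose were performed using paired t test". For the treatment effect it then says that "we constructed a mixed effect models with random slope by accounting for within-subject correlation". On covariates: "All the models were adjusted for age, gender, preoperative Lund-Mackay score, preoperative Lund-Kennedy score, and medication use". On surgery time: "Surgery time was found to be right-skewed; therefore, it was log-transformed in the model", and "the regression coefficient was exponentiated to represent the percentage difference".

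Protocol section 2a fixes the data structure. Each patient receives the active infiltration on one side and saline on the other. For two outcomes, "The Estimated blood loss on each side and the duration of the surgery on each side will also be recorded", so each patient contributes one value per side. The Wormald scale differs, because each video is "evaluated by 2 different otolaryngologists to give grading score for surgical field of view". That can give two values per side, and the SAP does not say whether the two grades are averaged or modelled separately.

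**The concern.** With two values per patient there is little room for random effects. An intercept and a slope on treatment for each of 38 patients make 76 random effects for 76 rows, so the variance components cannot all be determined and the fit might fail. If the slope is the only random term, the usual codings cannot represent a positive correlation between the two sides, and the benefit of the split-nose design is lost.

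The model matters. It is the SAP's stated estimator of the treatment effect, its only covariate-adjusted analysis, and the only analysis of surgery time said to be on the log scale. The wording alone does not tell a reader which model to reproduce.

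**Working it through.** **Inputs.** n = 38 patients (SAP section 1), two sides each, one surgery-time value per side (Protocol section 2a): 38 × 2 = 76 rows. The documents give no between-side correlation ρ, so 0.3, 0.5 and 0.7 are assumptions. The SAP's 82% power is for the Wormald scale. It cannot be reproduced without an effect size, SD and correlation, and nothing below uses it.

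**Step 1: what two values per patient can determine.** Let the intercept variance be A, the slope variance B, their covariance C and the residual variance E, with treatment coded 0/1.
- Variance, control side: A + E
- Variance, active side: A + 2C + B + E
- Covariance between sides: A + C

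Three moments cannot fix four parameters, so the variance split is not identifiable. The treatment estimate depends only on the side difference, whose variance is (A + E) + (A + 2C + B + E) − 2(A + C) = B + 2E. That quantity is identified, and SE² = (B + 2E)/n whichever split the software returns.

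**Step 2: numerical check.** One simulated set of 38 pairs gave:

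| Model | B | E | √((B + 2E)/38) |
|---|---|---|---|
| Patient intercept | 0 | 0.0969 | 0.0714 |
| Intercept + correlated slope | 0.0463 | 0.0738 | 0.0714 |
| Slope only, 0/1 | 0.0567 | 0.2147 | 0.1131 |

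The paired t test gave 0.0714, and all three models gave the same point estimate, −0.136. In further refits with intercept plus slope (38 pairs, 60 data sets per assumed correlation), every fit converged without warning and the SE equalled the paired SE. An intercept with an independent slope under 0/1 coding also gives a ratio of 1.00. So does treatment entered as a two-level factor with no separate intercept and an unstructured covariance, which is the correlated model in another form.

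**Step 3: the slope-only reading.** With 0/1 coding the implied between-side covariance is 0. With −0.5/+0.5 coding it is −0.25B, so never positive. For equal side variances s², the model's SE² is 2s²/n against a paired SE² of 2s²(1 − ρ)/n, a ratio of 1/√(1 − ρ):
- ρ = 0.3: 1/√0.7 = 1.20
- ρ = 0.5: 1/√0.5 = 1.41
- ρ = 0.7: 1/√0.3 = 1.83

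With 1/2 coding part of the correlation is recovered, and the ratios are 1.07, 1.17 and 1.36. The data set in Step 2 agrees: its intercept variance is 0.1462, so its correlation is 0.1462/(0.1462 + 0.0969) = 0.601. Then 1/√(1 − 0.601) = 1.58, and 0.1131/0.0714 = 1.58. The error is conservative: under 0/1 coding, simulated type I error was about 1.8%, 0.6% and 0.05% at the three correlations, against a nominal 5%.

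**Step 4: Wormald scores.** If the two grades are kept as separate rows, each patient has 2 × 2 = 4 rows, and an intercept plus a treatment slope can be estimated. Let T be the side-within-patient variance and E the variance of a single grade. The correct SE² is (2T + E)/n. A patient intercept alone pools three within-patient contrasts and gives about (2T/3 + E)/n. If T = E (an assumption), the ratio is √((5/3)/3) = 0.745, an SE about 25% too small. Simulation gave about 24%. Intercept plus slope gave the correct SE.

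**The case for a change.** The strongest contrary case is about reproducibility. A SAP should let a second analyst fit the same model. Here the readings run from the paired standard error to 1.83 times it at an assumed correlation of 0.7, and coding alone moves the answer if the slope stands by itself. The paired t tests are only a partial safeguard. They are unadjusted, and the SAP does not say whether surgery time was logged for them. Protocol section 8h limits Lund-Mackay asymmetry to a difference below 2, but nothing limits Lund-Kennedy asymmetry, so the adjusted and paired results need not coincide exactly.

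The omission stands: the random-effects structure is under-described. The inference to a flawed analysis does not. Slope-only with 0/1 or −0.5/+0.5 coding cannot do what the same sentence says the model does, whereas an intercept with a slope is what the phrase usually abbreviates. The SAP also reports models already built, so a possible failure to converge is conjecture. Replacing the phrase with a patient intercept would misreport the analysis if an intercept plus slope was fitted. If grader-level Wormald rows were used, it would replace a sound model with one whose standard error is too small.

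**Conclusion.** No change to the plan follows. This is missing detail that an analyst fills sensibly, with no gain from altering the model. Under the ordinary readings the treatment standard error for surgery time is 1.00 times the paired one. Only the division of variance between components is undetermined, and no stated result uses that division. A loss of precision, 1.20 to 1.83 times under 0/1 or −0.5/+0.5 coding, needs the slope to be the sole random term and the sides to be positively correlated. The documents do not show that such a model was fitted, and the error would be conservative.

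The exact equality assumes complete pairs and no covariate that differs between sides. Age and gender meet that condition. Side-specific Lund-Mackay or Lund-Kennedy scores could cause small departures. The correlations are assumed. The SAP's 82% power says nothing about surgery time, for which the documents give no power, effect size or SD.

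### Side of the nose is what is randomised, but no planned analysis has a left/right term; the test stays valid on average, yet a cheap gain in precision and robustness is missed

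*SAP*

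**What the plan says.** Protocol section 2a (Procedures) sets up a within-patient comparison: "patient will receive 1% xylocaine with adrenaline (1:100,000) on one side and saline on the contralateral side". The allocation rule follows in the same place: "they will be randomized to which side receive which solution for infiltration". Every participant is therefore either drug-left/saline-right or drug-right/saline-left. No blocking or other device to equalise the two groups is described.

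SAP section 1 gives the power statement for the Wormald score, "A sample size of 38 patients in total would give the power of 82% with type I error of 0.05", but no effect size, SD or simulation model. It then names two kinds of analysis. The unadjusted one is "The comparisons of clinical variables (all continuous) between both sides of the nose were performed using paired t test". The other is a mixed model with a random slope, for which "All the models were adjusted for age, gender, preoperative Lund-Mackay score, preoperative Lund-Kennedy score, and medication use". Anatomical side is in neither. Protocol section 8a plans a "total of 40 participants overall".

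**The concern.** The design is a two-period crossover with anatomical side in the place of period. The paired t test pools the drug-minus-saline differences of the two groups. If left and right differ on average for any reason other than the drug, that difference enters with a plus sign in one group and a minus sign in the other. It then counts as noise and, when the groups are unequal in size, part of it counts as drug effect.

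Nothing already planned removes it:

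- Age, gender and medication use are constant within a patient and cannot absorb a left-right contrast.
- The two disease scores could absorb disease-related asymmetry if entered per side, which the SAP does not state.
- The random slope would take up the contrast as variation in drug effect between patients, which is the added noise itself.
- The exclusion of patients whose Lund-Mackay scores differ by 2 or more between sides limits disease asymmetry only.

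At stake are some power and the trustworthiness of the estimate under the split actually obtained. The validity of the randomised comparison is not in question.

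**Working it through.** **Inputs.** From the SAP: n = 38, power 82%, α = 0.05 (taken as two-sided). From the protocol: side randomised within patient, balance not stated, so both simple 50:50 allocation and a forced 19:19 split are examined. Assumed: δ = 0, 0.1, 0.25 and 0.5, in units of the SD of the within-patient difference.

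**The plan's figure.** The 82% cannot be rebuilt independently, because its effect size and SD are not given. Solving backwards with the noncentral t distribution (37 df), 82% corresponds to a mean paired difference of τ = 0.479 SD. With the 40 participants the protocol plans, the same effect gives 84%. The rest uses n = 38.

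**Model.** For patient i, let D be drug side minus saline side, z = +1 if the drug is on the left and −1 if on the right, and δ the mean left-minus-right difference without drug:

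D_i = τ + δ z_i + e_i, SD(e) = 1.

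**Effect on the standard error.** Omitting z raises the variance of D from 1 to about 1 + δ². The SE goes from 1/√38 = 0.162 to about √1.0625/√38 = 0.167 at δ = 0.25 and √1.25/√38 = 0.181 at δ = 0.5. Simulated mean SEs are 0.161, 0.166 and 0.180.

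**Shift given the split.** The mean of D is displaced by δ(nL−nR)/n.

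- 22:16: 6/38 = 0.158, so 0.039 SD at δ = 0.25 (8% of 0.479) and 0.079 SD at δ = 0.5 (16%). A split this uneven or worse has probability 42% under simple allocation.
- 24:14: 10/38 = 0.263, so 0.066 SD (14%) and 0.132 SD (27%). Probability of this or worse: 14%.

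The sign of nL−nR is random, so the shift averages to zero over allocations.

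**Simulation.** The paired t test (37 df) is compared with the regression of D on z (36 df), whose intercept is the drug effect. Power at τ = 0.479:

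| δ | Simple, no term | Simple, with term | 19:19, no term | 19:19, with term |
|---|---|---|---|---|
| 0 | 82% | 81% | 82% | 82% |
| 0.1 | 82% | 81% | 82% | 82% |
| 0.25 | 80% | 81% | 80% | 82% |
| 0.5 | 73% | 81% | 75% | 82% |

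Type I error at τ = 0:

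| δ | Simple, all splits, no term | Splits 24:14 or worse, no term | 19:19, no term |
|---|---|---|---|
| 0.1 | about 5% | about 5% | about 5% |
| 0.25 | about 5% | about 7% | 4.3% |
| 0.5 | about 5% | 11–12% | 2.9% |

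With the term, type I error is about 5% in every cell.

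**Price of the term when δ = 0.** At 19:19 only the degree of freedom is lost: 82.0% becomes 81.9%. Under simple allocation an uneven split also makes side and drug partly collinear, and power goes from about 82% to 81%. At δ = 0.1 the term still loses slightly more than it gains.

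**The case against.** The strongest reply is that a paired t test on a comparison randomised within the patient is standard and valid, and that the rest is preference. Most of this stands.

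A reader might infer from the missing term that the planned test has an inflated false-positive rate. It does not. Over all simple allocations the rate is about 5%, and with a forced even split it falls below 5%. The higher rates apply only within a minority of uneven splits.

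A reader might also infer that the trial's power is below the 82% it states. The documents do not show that. If the planning SD came from observed differences between sides, it already contains any left-right variation. Then the 82% stands for the planned test, and the term would only add power.

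Nothing in either document says that left and right do differ. Surgeon handedness or instrument angle are possible causes, but neither is mentioned. A δ of 0.5 would exceed the drug effect the trial is sized to detect (0.479), so that row is an upper scenario rather than an expectation. At 0.25 the gain in power is only about 1 point under simple allocation, and at 0.1 there is none.

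What remains is that the trial is run once, with one realised split. The term protects the estimate under that split at a worst average cost of about one point of power.

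**Conclusion.** The omission is real and worth correcting, as a matter of precision and robustness. The randomised comparison is not invalidated, and neither inflated overall type I error nor a wrong 82% can be claimed from the documents.

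The benefit depends on δ, which is unknown: none at 0.1 SD, about 1 point of power at 0.25, about 8 points at 0.5, all under simple allocation. With the term, type I error also stays at 5% under the more uneven splits. These figures rest on the back-solved effect of 0.479 SD, a two-sided test, 38 analysed patients, normal differences, and a planning SD that excludes left-right variation.

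**What to change.** - Add a fixed effect for anatomical side (left/right) to every mixed model.
- Replace each paired t test, or accompany it, with the regression of the drug-minus-saline difference on the side treated, coded ±1, on n−2 df. The intercept estimates the drug effect.
- Report how many patients had the drug on the left and how many on the right, so that the size of any possible shift can be judged.

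The side treated is fixed by the allocation, so no new data are needed. The cost is one degree of freedom and, if there is no left-right difference, about 1 point of power under simple allocation (0.1 point at 19:19).

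The SAP is in the past tense and reports a feature of the observed surgery times, so it appears to have been written with data in hand. In that case, keep the paired t test beside the new analysis and label the term as added later. Balancing the allocation list is worth asking for only if enrolment has not begun.

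### Does calling the exponentiated surgery-time coefficient a percentage difference, with no stated scale for the paired t test, require a change to the SAP?

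*SAP*

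**What the plan says.** Protocol section 2a (Procedures) makes surgery time a side-level measurement: "The Estimated blood loss on each side and the duration of the surgery on each side will also be recorded". It sets no analysis for it.

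The SAP (1. Statistical Methods) has three relevant statements:

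- The side-to-side test: "The comparisons of clinical variables (all continuous) between both sides of the nose were performed using paired t test". No variable is named and no transformation is mentioned.
- The treatment effect: "To estimate the effect of 1% lidocaine with 1:100,000 epinephrine, we constructed a mixed effect models with random slope", adjusted for five covariates.
- The handling of skewness and the effect measure, once surgery time had proved right-skewed: "it was log-transformed in the model, and the regression coefficient was exponentiated to represent the percentage difference".

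The only design figure is for the Wormald scale: "A sample size of 38 patients in total would give the power of 82% with type I error of 0.05". No SD, within-patient correlation or target effect is given for surgery time.

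**The concern.** Two things look wrong on first reading.

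**The label.** Exponentiating a coefficient from a log-outcome model gives a ratio. With no effect the ratio is 1, whereas a percentage difference is 0. Taken literally, the SAP reports one quantity under the name of another, and a reader could misread the estimate and its confidence limits.

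**The scale of the t test.** The SAP recognises that surgery time is skewed but mentions the log transform only for the model. If surgery time is among the clinical variables compared by paired t test, the natural inference is that raw minutes were tested. The unadjusted test would then address a difference in arithmetic means and the model a ratio of geometric means. The two could fall on opposite sides of 0.05, with no stated rule on which one counts.

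At stake would be how one additional outcome is reported and, in some data sets, whether its two analyses agree.

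**Working it through.** **Step 1: the plan's own figure.** The 82% power with 38 patients cannot be reproduced, because the SAP gives no effect size, SD or correlation. Solving back with a two-sided paired t test at 0.05 and n = 38 gives an implied standardized paired difference of about 0.479. That figure belongs to the Wormald scale and has no bearing on surgery time.

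**Step 2: the label.** Let b be the treatment coefficient on log time. Then

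- ratio of geometric means = exp(b)
- percentage difference = 100 × (exp(b) − 1)

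| b | exp(b) | Percentage difference |
|---|---|---|
| −0.2231 | 0.80 | −20% |
| −0.10 | 0.905 | −9.5% |
| −0.05 | 0.951 | −4.9% |
| 0 | 1 | 0% |
| 0.10 | 1.105 | +10.5% |

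The second and third columns carry the same information. The conversion is increasing in b, so both confidence limits convert in the same way. An interval for b excludes 0 exactly when the ratio interval excludes 1 and the percentage interval excludes 0. The p-value is the same in all three forms.

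**Step 3: validity of a raw-minutes t test.** A paired t test needs roughly normal within-patient differences, not symmetric times. Assumed inputs: 38 pairs of lognormal times and no true effect.

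- Log SD 0.3 to 0.6, correlation 0.5 to 0.7: raw-scale type I error 4.7% to 5.1%.
- Log SD 0.4 to 0.8, correlation 0.3 to 0.8: raw-scale type I error 4.0% to 5.0%, against 4.7% to 5.1% on the log scale.

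The raw test holds its level or is slightly conservative.

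**Step 4: power.** This depends on the model assumed.

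- *Proportional effect, lognormal times* (log SD 0.3 to 0.6, correlation 0.5 to 0.7), with the effect set for 82% power on the log scale: raw-scale power is 79–80% at log SD 0.3, 77–78% at 0.4 and 71–72% at 0.6. The two tests reach different decisions in about 6% to 15% of trials. A wider range (log SD up to 0.8, correlation 0.3 to 0.8) at a ratio of 0.8 gives 0.2% to 25%.
- *Shift in minutes*, with skewed patient-level times (skewness 1.4 to 3.6) and additive normal noise between sides: the raw test has about 82% power and the log test 77–80%. The correlations here are high, 0.82 to 0.98.

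The ordering reverses between the two models, and the size of the gap follows the assumptions. The documents give nothing to choose between them.

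**Step 5: what a log-scale t test would add.** In 60 simulated data sets with one time per side, a random-intercept model on log time, adjusted for five patient-level covariates, gave the same treatment coefficient as the log paired t test (difference below 1e-15). Standard errors agreed within 0.002%. Covariates that are constant within a patient cancel from a side-to-side contrast, so the log t test would mostly repeat the model.

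**The case for a change.** The strongest case for a change is that an analysis plan should let a second analyst reproduce the reported number, and read literally this one does not: it stops at exp(b) and calls the result a percentage. The t-test sentence describes its variables as all continuous and compares them between sides, and surgery time fits that description. A reader who knows that time is skewed and that logs were used for the model may fairly ask what the t test used. Under lognormal times the two scales can disagree often enough to notice, and one sentence would settle it.

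Part of this stands. exp(b) is a ratio, and the wording is loose. The scale of any surgery-time t test is unstated.

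The rest does not carry. The t-test sentence follows directly on the summary of demographics and baseline factors, does not name surgery time, and is followed by the sentence that gives estimation of the treatment effect to the mixed model. A raw-minutes test of surgery time is therefore an inference about what was done. The disagreement rates assume a proportional lognormal effect, and the 82% power used to set that effect was borrowed from the Wormald calculation. Two valid, correlated tests will also split near 0.05 at times without either being wrong.

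**Conclusion.** No change to the plan follows.

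- **Label:** this is shorthand. A ratio of 0.905 does represent a 9.5% reduction, and the last step is one that any analyst supplies when writing the result. The documents contain no mislabelled estimate, and no p-value or conclusion changes.
- **Scale of the t test:** this is a detail left open for an analysis that the SAP does not state for surgery time. Raw minutes would give a valid test of a readable quantity, the difference in mean minutes. Logs would give a ratio. For an additional outcome that is a fair trade-off.
- **Basis for inference:** the SAP already estimates the effect from the adjusted model, in which surgery time is logged. Replacing a raw t test with a log one would largely duplicate that model and remove the only test in minutes.

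The arithmetic on the label needs no assumption about the data. The type I error figures rest on lognormal times with 38 pairs. The match between the log t test and the model was checked for a random intercept with patient-level covariates. The random slope that the SAP names, and side-specific covariates, were not simulated. The power comparison has no fixed direction without data on surgery time, so it gives no ground for preferring either scale.

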Video recording will be performed in the study (our department usually has all the surgeries recorded as a routine procedure). This will be reviewed by 2 otolaryngologists at Stanford's university (attendings or rhinology fellows). The otolaryngologist reviewing and grading the video will be blinded to which side of the sinus surgery was performed under only topical adrenaline or with the combination of both topical and infiltration of adrenaline. The video given will be labeled by the number and not by name of the patient and the video will be secure with passcode lock external hard disk.

e. Alternative Procedures or Courses of Treatment

Many different methods and many different agents have been used to help reduce bleeding in endoscopic sinus surgery. Currently, adrenaline has become the consensus as the best agent used for this purpose; however, there is no one consensus method of delivery, each center practices according to their experience for the best of the patients. At our center, half of the team use only topical adrenaline before the surgery and the other half combine infiltration of xylocaine with adrenaline with topical adrenaline. Therefore, the alternative at our center depends on the surgeon's experience between topical adrenaline only and topical adrenaline combine with infiltration. In this study the participant instead of one or the other will get a combination of pure topical on one side and combine topical with infiltration on the other side of the nasal cavity. Using both topical and infiltration of adrenaline may result in less bleeding and better field of view, however infiltration of adrenaline may have potential side effect e.g. cardiovascular and central nervous system side effects. However, xylocaine with adrenaline is a widely used anesthesia and administering at appropriate dosage and route under an extremely well controlled environment as being under general anesthesia in the operating room where all patient's vital signs are monitored shouldn't be risky. Now that topical adrenaline is more

widely used than before we want to examine the benefit of additional infiltration of adrenaline to the surgical field of view to determine the best optimal practice for endoscopic sinus surgery.

f. Will it be possible to continue the more (most) appropriate therapy for the participant(s) after the conclusion of the study?

After the study, the participants will be able to use any therapy that is appropriate for them.

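### Does the SAP need a stated rule for turning the two graders' Wormald scores into the value analysed?

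*SAP*

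**What the plan says.** Protocol section 2a (Procedures) provides for two scores per operated side: "The Video of the surgery will be evaluated by 2 different otolaryngologists to give grading score for surgical field of view". Section 2d (Use of Audio and Video Recordings) adds who the graders are, "This will be reviewed by 2 otolaryngologists at Stanford's university (attendings or rhinology fellows"), and that they do not know which side was infiltrated. Neither section describes averaging, consensus or adjudication.

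The SAP is a single paragraph, section 1 (Statistical Methods). Its power statement is "A sample size of 38 patients in total would give the power of 82" per cent at a type I error of 0.05, and the target is "to detect the difference in Wormald scale between the 2 groups". Two analyses follow. The first is a paired comparison: "The comparisons of clinical variables (all continuous) between both sides of the nose were performed using paired t test". The second is a model: "we constructed a mixed effect models with random slope by accounting for within-subject correlation". The two graders are mentioned only for the reliability calculation ("We performed reliability testing for the Wormald scale graded by 2 graders, by calculating the intraclass correlation coefficient (ICC"), with a 95% confidence interval).

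**The concern.** The Wormald score carries the power statement, yet its analysed form is not defined. Each patient has four scores (two sides, two graders), and a paired t test needs one value per side. An ICC describes agreement. It is compatible with averaging the grades, and equally with analysing one grader and using the second only to check reliability.

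Three things could be at stake.

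- **Precision.** A mean of two graders is less noisy than one grader, so a reader cannot tell which score the 82% describes.
- **Selective reporting.** The SAP is written in the past tense and already reports a feature of the data ("Surgery time was found to be right-skewed"). Nothing on the page shows that the scoring rule was set before the grades were seen.
- **Unit of analysis.** If both graders' scores entered the t test as separate independent pairs, the standard error would be too small. One could also read the random slope as a sign that both graders' rows were modelled.

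**Working it through.** **Inputs.** From the SAP: n = 38, power 82%, type I error 0.05. Assumed: a two-sided test, since sidedness is not stated, and r, the correlation between the two graders' side-to-side differences, taken as 0.5 to 0.9. The documents give no effect size, SD, within-patient correlation, ICC or simulation model.

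**Step 1: the plan's figure.** The 82% cannot be reproduced from the documents. It can only be inverted. For a paired t test with 37 degrees of freedom and noncentrality dz × √38, 82% power requires dz = 0.479. The normal approximation gives (1.960 + 0.915)/√38 = 0.466, which is consistent.

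**Step 2: mean against one grader.** With equally variable graders, Var(mean of two) = Var(one) × (1 + r)/2. The standard error with one grader is therefore √(2/(1 + r)) times that with the mean. The standardised difference is divided by this factor when moving from mean to one grader, and multiplied by it in the other direction.

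| r (assumed) | SE ratio, one grader to mean | Power with one grader if 82% is for the mean | Power with the mean if 82% is for one grader |
|---|---|---|---|
| 0.5 | 1.15 | 70% | 91% |
| 0.6 | 1.12 | 73% | 90% |
| 0.7 | 1.08 | 76% | 88% |
| 0.8 | 1.05 | 78% | 86% |
| 0.9 | 1.03 | 80% | 84% |

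Example at r = 0.5: 0.479/1.155 = 0.415, which gives 70% power.

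**Step 3: why the ICC would not pin this down.** Split the score variance into patient, side-within-patient and grader error. The single-grader ICC is (patient + side)/(patient + side + error). Patient variance cancels in the side difference, so r = side/(side + error). Hold error at 0.3 and patient + side at 1.5, so that the ICC is 1.5/1.8 = 0.83 throughout, and vary only the split:

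| Patient / side variance | r | Power with one grader |
|---|---|---|
| 0.5 / 1.0 | 0.77 | 77% |
| 1.0 / 0.5 | 0.63 | 74% |
| 1.3 / 0.2 | 0.40 | 67% |
| 1.4 / 0.1 | 0.25 | 62% |

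The same ICC is compatible with 62% to 77%. The quantity that matters is agreement on the side difference, and the documents say nothing about it.

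**Step 4: does the random slope imply grader-level rows?** Code treatment 0/1. Let a be the intercept variance, b the slope variance (uncorrelated with the intercept) and e the residual variance. With one value per side, Var(untreated) = a + e, Var(treated) = a + b + e and Cov = a. Hence a = Cov, e = Var(untreated) − Cov and b = Var(treated) − Var(untreated): three equations, three unknowns. Only an added intercept-slope covariance makes a fourth unknown, and the SAP names no covariance structure. The same model description also covers surgery time, which protocol section 2a records once per side and which has no graders. The slope is therefore no evidence that both graders' rows were used.

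**Step 5: the separate-rows case.** If 76 differences (38 × 2) were treated as independent, simulated type I error would be about 0.11 at r = 0.5 and 0.16 at r = 0.9. The SAP describes no such analysis. It counts patients, pairs the two sides of the nose and allows for within-subject correlation in the model. If both grades were stacked in a model with patient intercept and treatment slope, simulated fits gave a median standard error 1.000 times that of the paired t test on the mean. Under the named model type, stacking and averaging come to the same thing.

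**The case for a change.** The strongest case for acting is that the powered outcome has no operational definition, the remedy is a sentence or two, and the past tense leaves open that the rule was chosen after the scores were seen. With no true effect, and under assumed variances giving a single-grader ICC of 0.91 to 0.71, reporting the smallest p-value from grader A, grader B and their mean would raise type I error to between 8.2% and 10.1%.

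What stands is the textual point: neither document states the rule, and the power statement cannot be tied to a particular score. The rest carries less weight. The smallest-p figures describe a practice for which the documents give no sign. The past tense runs through the whole SAP, and the remark on skewness concerns surgery time, not the Wormald grades. Low cost is no argument by itself when the missing detail leaves every ordinary choice valid.

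**Conclusion.** This is a narrow reporting omission that analysts fill sensibly. Mean, single grader and consensus are all legitimate if fixed in advance, and each then holds the 5% error rate. None changes the design, the paired comparison or the model. The default for two blinded graders is to average, and naming the analysed score belongs to the ordinary write-up of results.

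The only effect shown is on precision. Relative to a nominal 82%, one grader in place of the mean gives roughly 70% to 80% power, and the mean in place of one grader roughly 91% to 84%. These figures assume a two-sided paired t test at n = 38, equally variable graders and r between 0.5 and 0.9. With weaker agreement on the side difference (r = 0.25) the single-grader figure falls to 62%. The documents cannot say where in this span the trial lies, or which score the 82% used. No change to the plan is needed.
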